Tumor assessments or monitoring will be performed by the investigators at Screening Visit, end of treatment Cycle 3, and end of treatment Visit per their clinical practice. International Neuroblastoma Response Criteria (INRC) (Brodeur et al 1993) is recommended as a reference for response evaluation (Section 8.4) in patients evaluable for tumor assessment. Refer to Section 7.6 for additional considerations regarding treatment continuation and withdrawal. Patients who, at the time of progression, have an ongoing AE that leads to treatment discontinuation and who have completed the scheduled Safety Follow-up Visit will be followed up until the event resolves, the investigator assesses the event as stable, the patient is lost to follow-up, or the patient starts a new anticancer therapy, end of study, whichever comes first.

Patients who have discontinued study drug(s) should return to the site for an End-of-Treatment (EOT) Visit as detailed in Section 7.4. After the EOT Visit, patients will have scheduled follow-up visits for safety (Appendix 1).

Study procedures and assessments are further detailed in Section 7 and Section 8, respectively, and the Schedule of Assessments can be found in Appendix 1.

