5.4. Dose Delay or Modification

Dose modification

This protocol allows some alteration from the currently outlined infusion schedule of dinutuximab beta, but the maximum cumulative exposure will not exceed 100 mg/m²/cycle.

Based on the Investigator's evaluation of the severity of adverse drug reactions to dinutuximab beta, patients may undergo a dose reduction of 50% or a temporary interruption of the infusion. As a consequence, either the infusion period is prolonged or, if tolerated by the patient, the infusion rate may be increased up to 3 mL/h (continuous infusion), in order to administer the total dose.

Regarding the dose modification of 13-cis-RA, please refer to local label of 13-cis-retinoic acid.

Table 3: Recommended Dinutuximab Beta Dose Modification

Adverse reaction	Severity	Treatment modification
Any	Grade 1 or 2	Decrease infusion rate to 50%. After resolution, resume infusion at original rate.

Hypersensitivity reaction	eg, Hypotension	Interrupt infusion and administer supportive measures. After resolution, resume infusion at original rate.
Dilated pupils with sluggish light reflex ± photophobia		Interrupt infusion. After resolution, resume infusion at 50% rate.
Any	≥ Grade 3	Interrupt infusion and administer supportive measures. Resume infusion at 50% rate if adverse drug reaction (ADR) resolves or improves to Grade 1 or 2 within 3 days of onset. If 50% dose reduction is tolerated for ≥ 1 day, consider advancing infusion to full rate as tolerated. If toxicity (≥ Grade 3) recurs at 50% dose reduction, treatment should be discontinued. If toxicity (≥ Grade 3) recurs while at 100% infusion rate, stop infusion and reduce dose to 50% if toxicity resolves or improves to ≤ Grade 2 within 3 days of onset. Do not increase dose to 100% again.
Capillary leak syndrome		Interrupt infusion and administer supportive measures. Resume at 50% rate if ADR resolves or improves to Grade 1 or 2.
Capillary leak syndrome requiring ventilator support; allergic reaction (anaphylaxis), skin toxicity, severe neuropathic pain, any other Grade 4 toxicity (which does not recover to Grade 1 or 2 or baseline within 5 weeks)	Grade 4	Discontinue infusion. Contact sponsor to confirm if patient may continue infusion at the start of the subsequent cycle.

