7.6. Discontinuation From Study Treatment or From the Study

7.6.1. Patient Discontinuation From Study Treatment (End of Treatment for an Individual Patient)

Patients have the right to discontinue study drug at any time for any reason. In addition, the investigator has the right to discontinue a patient from study drug at any time. Patients who discontinue study drug for reasons other than relapse or progressive disease (PD) should be followed for assessments of preliminary anticancer activity (Section 8.4) and safety (Section 8.2), if possible.

The primary reason for discontinuation from study drug should be documented on the appropriate eCRF. Patients may discontinue study drug for reasons including but not limited to the following:

- Relapse
- PD
- AE
- Patient decision
- Pregnancy
- Any medical condition that the investigator or sponsor determines may jeopardize the patient's safety if he or she were to continue the study drug
- Use of any concurrent anticancer therapy, including chemotherapy, hormonal therapy, immunotherapy, standard or investigational agents (including Chinese [or other Country] herbal medicine and Chinese [or other Country] patent medicines) for the treatment of cancer [regardless of cancer type])
- Patient noncompliance
 - Study site staff should first counsel patients who are significantly noncompliant (eg, missing 2 treatment cycles) on the importance of study drug compliance and drug accountability. The investigator may, in consultation with the medical monitor, discontinue patients from treatment who are consistently noncompliant.

Treatment with dinutuximab beta should be permanently discontinued if the following toxicities occur:

• Grade 3 or 4 anaphylaxis

- Prolonged Grade 2 peripheral motor neuropathy
- Grade 3 peripheral neuropathy
- Grade 3 vision eye toxicity
- Grade 4 hyponatremia (< 120 mEq/L) despite appropriate fluid management
- Recurrent or Grade 4 capillary leak syndrome (requires ventilator support)

If dinutuximab beta or 13-cis-RA is discontinued permanently before cycle 5 for reasons other than relapse or PD, the other drug could be continued per the study protocol.

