9.6. Risks Associated With Dinutuximab Beta

Hypersensitivity Reactions

Severe infusion-related reactions including cytokine release syndrome (CRS) and anaphylactic and hypersensitivity reactions may occur despite the use of premedication. Occurrence of a severe infusion-related reaction (including CRS) requires immediate discontinuation of dinutuximab beta therapy and may necessitate emergency treatment.

CRS frequently manifests itself within minutes to hours of initiating the first infusion and is characterized by systemic symptoms such as fever, hypotension, and urticaria.

Anaphylactic reactions may occur as early as within a few minutes of the first infusion with dinutuximab beta and are commonly associated with bronchospasm and urticaria.

Treatment of Hypersensitivity Reactions

Antihistamines, epinephrine (adrenaline), and prednisolone for intravenous administration should be immediately available at the bedside during administration of dinutuximab beta to manage life-threatening allergic reactions. Treatment for such reactions should include prednisolone and epinephrine administered by intravenous bolus every 3 to 5 minutes as necessary according to clinical response. In case of bronchial and/or pulmonary hypersensitivity reaction, epinephrine (adrenaline) inhalation is recommended and should be repeated every 2 hours according to clinical response.

Capillary Leak Syndrome

Capillary leak syndrome (CLS) is characterized by a loss of vascular tone and extravasation of plasma proteins and fluid into the extravascular space. CLS usually develops within hours after initiation of treatment, whereas clinical symptoms (ie, hypotension, tachycardia) are reported to occur after 2 to 12 hours. Careful monitoring of circulatory and respiratory function is required.

Neurological Disorders of The Eye

Eye disorders may occur as dinutuximab beta binds to optic nerve cells. No dose modification is necessary in the case of an impaired visual accommodation that is correctable with eyeglasses, as long as this is judged to be tolerable.

Treatment must be interrupted in patients who experience Grade 3 vision toxicity (ie, subtotal vision loss per toxicity scale). In case of any eye problems, patients should be referred promptly to an ophthalmology specialist.

Peripheral Neuropathy

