Occasional occurrences of peripheral neuropathy have been reported with dinutuximab beta. Cases of motor or sensory neuropathy lasting > 4 days must be evaluated and non-inflammatory causes such as disease progression, infections, metabolic syndromes, and concomitant medication should be excluded.

Treatment should be permanently discontinued in patients experiencing any objective prolonged weakness attributable to dinutuximab beta administration. For patients with moderate (Grade 2) neuropathy (motor with or without sensory), treatment should be interrupted and may be resumed after neurologic symptoms resolve.

Systemic Infections

Patients are likely to be immunocompromised as a result of prior therapies. As they typically have a central venous catheter in situ, they are at risk of developing systemic infection. Patients should have no evidence of systemic infection and any identified infection should be controlled before starting therapy.

Hematologic Toxicities

Occurrence of hematologic toxicities such as erythropenia, thrombocytopenia, or neutropenia has been reported with dinutuximab beta. Grade 4 hematologic toxicities improving to \leq Grade 2 or baseline values by start of next treatment course do not require dose modification.

Laboratory Abnormalities

Regulatory monitoring of liver function and electrolytes is recommended.

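### Grade 3 vision toxicity: Protocol 7.6.1 stops dinutuximab beta permanently, 9.6 only interrupts it, and Table 3's general row allows a restart

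*Protocol*

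**What the plan says.** Three places in the protocol bear on the same event.

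- **Section 7.6.1** introduces a list with "Treatment with dinutuximab beta should be permanently discontinued if the following toxicities occur", and one entry is "Grade 3 vision eye toxicity". The entry carries no condition about recovery or duration.
- **Section 9.6, Neurological Disorders of The Eye**, says: "Treatment must be interrupted in patients who experience Grade 3 vision toxicity (ie, subtotal vision loss per toxicity scale". It adds prompt referral to an ophthalmologist for any eye problem. It is silent on restarting and does not refer to 7.6.1.
- **Section 5.4, Table 3**, is presented as recommended dose modification. Vision loss has no row. The row for any reaction of Grade 3 or higher starts with interruption and continues: "Resume infusion at 50% rate if adverse drug reaction (ADR) resolves or improves to Grade 1 or 2 within 3 days of onset". The only eye row concerns dilated pupils, and its instruction is "Interrupt infusion. After resolution, resume infusion at 50% rate".

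Sections 3.1 and 7.3 both contain a general pointer: "Refer to Section 7.6 for additional considerations regarding treatment continuation and withdrawal". Section 9.1.3 directs the reader to 9.6 for the measures against anticipated toxicities.

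**The concern.** A stopping rule should give one answer wherever the investigator looks it up. Here the answer depends on the section consulted. The eye is a named target of toxicity, which 9.6 attributes to antibody binding to optic nerve cells, and the event in question is subtotal vision loss in a population enrolled from 12 months of age. Appendix 1 schedules ophthalmologic examinations only at screening, end of treatment and safety follow-up, so during treatment the decision rests on the written rule and on unscheduled referral. The referral is a real safeguard, but it does not settle whether the drug may be restarted.

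There is also a smaller reporting consequence. SAP Section 6.6.2 counts adverse events leading to treatment discontinuation separately from those leading to dose interruption. Two sites following different sections would place the same event in different rows of a primary safety summary.

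**Working it through.** The plan states no figure on this point, so the check is a comparison of texts.

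**Step 1. The three instructions side by side**

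| Source | First action | May the drug be restarted? | Cites 7.6.1? |
|---|---|---|---|
| 7.6.1 list | Permanent stop | No | – |
| 9.6, eye paragraph | Interrupt | Not stated | No |
| Table 3, general row, Grade 3 or higher | Interrupt | Yes, at half rate, if Grade 1 or 2 or resolved within 3 days | No |

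**Step 2. Can interruption in 9.6 be read as a permanent stop?** Not easily. The next paragraph of 9.6, on peripheral neuropathy, uses both terms for different actions. For prolonged weakness it says "Treatment should be permanently discontinued in patients experiencing any objective prolonged weakness attributable to dinutuximab beta administration". For Grade 2 neuropathy it says "treatment should be interrupted and may be resumed after neurologic symptoms resolve". Within 9.6, then, an interruption is something that can be followed by resumption.

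**Step 3. Which pairs are compatible?** Interrupting and then stopping for good satisfies both 9.6 and 7.6.1. Resuming under Table 3 cannot satisfy 7.6.1. The direct contradiction is therefore between Table 3 and 7.6.1; 9.6 leaves the question open where it should close it.

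**Step 4. Does any text set precedence?** The pointers in 3.1 and 7.3 describe 7.6 as a source of additional considerations. They do not say that it overrides Table 3 or 9.6, and neither of those sections carries a pointer of its own. Table 3 does have entries for some reactions that also appear in 7.6.1, such as anaphylaxis and capillary leak needing ventilation. A site could reasonably assume that exceptions to the general row are shown in the table.

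**Step 5. Dose in dispute for one affected patient.** Inputs are up to 5 cycles at 100 mg/m² per cycle (Section 5.2.1). Onset in Cycle k leaves 5 − k later cycles, so the planned later dose is at most (5 − k) × 100 mg/m²:

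- k = 1: 4 × 100 = 400 mg/m²
- k = 2: 3 × 100 = 300 mg/m²
- k = 3: 2 × 100 = 200 mg/m²
- k = 4: 1 × 100 = 100 mg/m²
- k = 5: 0 × 100 = 0 mg/m²

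The undelivered part of the current cycle comes on top. Under 7.6.1 both amounts are zero for every k. The figures are ceilings: they assume improvement within 3 days, no recurrence and completion of every remaining cycle at full dose.

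**The case against.** The strongest reply is that the protocol already contains the right rule and that ordinary reading finds it. Section 7.6.1 names the toxicity, whereas the Table 3 row is generic and only recommended. Several other entries in 7.6.1, such as Grade 3 peripheral neuropathy and Grade 4 hyponatremia, would also fall under that generic row, so the list has a purpose only if it overrides the row. Section 9.6 gives no permission to restart after vision toxicity, although it gives one explicitly for Grade 2 neuropathy, so its eye paragraph is incomplete rather than contradictory. Sections 3.1 and 7.3 do point to 7.6. Table 3 also limits the exposure: improvement must come within 3 days, and recurrence of Grade 3 or higher toxicity at half dose ends treatment. Finally, no statistical quantity changes.

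Most of this stands. Section 7.6.1 is probably the intended governing rule, a reader who holds all three sections together would probably reach the safe answer, and the dose ceilings should carry no weight in judging severity. But the precedence is inferred and not written. The step from a general row to an unlisted exception is left to an investigator managing an acute event, and the table being used at that moment gives the opposite instruction. That is a conflict between stated rules, not merely missing detail.

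**Conclusion.** The concern holds and should be fixed. For Grade 3 vision toxicity the protocol gives a permanent stop in 7.6.1, an interruption with no statement about restarting in 9.6, and a conditional restart under the general row of Table 3. Following Table 3 as written breaches 7.6.1.

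How many patients this would affect cannot be stated, because neither document gives an incidence of Grade 3 vision toxicity. The conclusion rests on reading the general row as covering any reaction not otherwise listed, which is what its label says. It concerns dinutuximab beta only, since 7.6.1 lets 13-cis-RA continue. The consequences are for patient safety and for consistent classification of the event; sample size, analysis sets and estimation are unaffected.

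**What to change.** Make 7.6.1 the governing rule and say so in both other places.

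1. In 9.6, change the eye paragraph so that Grade 3 vision toxicity requires immediate interruption and permanent discontinuation of dinutuximab beta, with a reference to Section 7.6.1.
2. In Table 3, add a row or footnote stating that the toxicities listed in 7.6.1, including Grade 3 vision toxicity, are exceptions to the general restart rule and that 7.6.1 prevails.

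If the sponsor's clinicians do intend to allow a restart after early recovery, the item should instead be removed from 7.6.1, so that only one rule remains.

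The cost is a protocol wording amendment and a notice to sites, with no added visit, procedure or patient. A patient whose vision would have recovered within 3 days may be stopped for good where a site would otherwise have restarted, but 7.6.1 already requires that.

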4.2. Exclusion Criteria

Patients who meet any of the following criteria will be excluded from this study:

- 1. Hypersensitivity to ≥ 1 component of dinutuximab beta antibody or against mouse proteins
- 2. Actively progressive disease (not stabilized) or recurrent disease at the time of inclusion into the study
- 3. Significant intercurrent illnesses and/or any of the following:
 - Symptoms of congestive heart failure or uncontrolled cardiac rhythm disturbance
 - Significant psychiatric disabilities or uncontrolled seizure disorders
 - Active infections or active peptic ulcer, unless these conditions are corrected or controlled
 - Clinically significant neurologic deficit or objective peripheral neuropathy (> Grade 2)
 - Clinically significant, symptomatic pleural effusions
- 4. Previous treatment with anti-GD2 antibody before enrolling in this study
- 5. Any condition that required systemic treatment with either corticosteroids or other immunosuppressive medication \leq 14 days before the first dose of study drug(s).
- 6. Concurrent treatment with any non-study anticancer therapies
- 7. Patients with active hepatitis C infection should be excluded. Note: Cured hepatitis C patients (as defined by a positive hepatitis C virus (HCV) antibody test and negative HCV RNA test) can be enrolled
- 8. Known history of HIV infection

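### For peripheral neuropathy, Table 3 contradicts Section 7.6.1 at Grade 3 and Section 9.6 at Grade 2 with a motor component, and no passage says which governs

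*Protocol*

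**What the plan says.** Three places in the protocol tell the site what to do with dinutuximab beta when peripheral neuropathy occurs.

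- **Section 5.4, Table 3.** The table has two generic rows for any adverse reaction. At Grade 1 or 2: "Decrease infusion rate to 50%. After resolution, resume infusion at original rate". At Grade 3 or above, the infusion is interrupted and then: "Resume infusion at 50% rate if adverse drug reaction (ADR) resolves or improves to Grade 1 or 2 within 3 days of onset". A later return to full rate may be considered if the half rate is tolerated. Hypersensitivity, pupil changes and capillary leak syndrome have rows of their own; peripheral neuropathy does not.
- **Section 7.6.1.** The list of toxicities requiring permanent discontinuation includes "Prolonged Grade 2 peripheral motor neuropathy" and "Grade 3 peripheral neuropathy". Neither item has an exception for recovery.
- **Section 9.6, Peripheral Neuropathy.** At Grade 2: "For patients with moderate (Grade 2) neuropathy (motor with or without sensory), treatment should be interrupted and may be resumed after neurologic symptoms resolve". On weakness: "Treatment should be permanently discontinued in patients experiencing any objective prolonged weakness attributable to dinutuximab beta administration". The only duration given is for work-up: "Cases of motor or sensory neuropathy lasting > 4 days must be evaluated".

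On entry, criterion 3 in Section 4.2 excludes "Clinically significant neurologic deficit or objective peripheral neuropathy (> Grade 2", so objective neuropathy at Grade 2 is not clearly barred.

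**The concern.** A clinician working from the dose-modification table and one working from the stopping list or the risk section would manage the same neuropathy differently. At Grade 2 with a motor component the drug is either running at half rate or not running. At Grade 3 it is either restarted or ended for good.

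Patient safety is the first thing at stake. The second is what the study reports. Safety and tolerability form a primary objective. Protocol Sections 10.2.1 and 10.2.2 and SAP Sections 6.6.1 and 6.6.2 tabulate interruptions, delays and discontinuations, and the SAP adds dose reductions. If the rule followed varies by site, those counts partly reflect which section was read. Section 11 provides for no study committee that could make handling uniform.

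**Working it through.** The plan gives no figure to reproduce, because this is a comparison of texts. The inputs are the two generic rows of Table 3 (Section 5.4), the two neuropathy items in Section 7.6.1, and the three neuropathy statements in Section 9.6 (evaluation, weakness, Grade 2). Taking them case by case:

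| Event | Table 3 | Section 9.6 | Section 7.6.1 | Result |
|---|---|---|---|---|
| (a) Grade 2 with motor component, not prolonged | Continue at half rate | Interrupt until symptoms resolve | Silent | Table 3 conflicts with 9.6 |
| (b) Grade 2 motor, prolonged | Continue at half rate; no time limit | Permanent stop if there is objective weakness attributable to the drug | Permanent stop | Table 3 conflicts with 7.6.1, and with 9.6 where weakness is present; threshold undefined |
| (c) Grade 2, purely sensory | Continue at half rate | Evaluate if longer than 4 days; no interruption rule | Silent | No clear conflict |
| (d) Grade 3, falling to Grade 2 or below within 3 days | Interrupt, then restart at half rate | No Grade 3 rule | Permanent stop | Direct conflict |
| (e) Grade 3, not improving within 3 days | Restart condition not met | No Grade 3 rule | Permanent stop | No restart under either |

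Three observations follow.

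1. The Grade 3 conflict is confined to case (d), because Table 3 allows a restart only when improvement comes within 3 days. In that case the patient may restart with residual Grade 2 neuropathy. If it has a motor component, that is the state in which 9.6 calls for interruption.
2. Sections 7.6.1 and 9.6 are compatible with each other as tiers: interrupt at Grade 2, stop if it is prolonged, stop at Grade 3. What they share is an undefined term. The 7.6.1 item is limited to Grade 2 motor neuropathy and the 9.6 weakness sentence names no grade, but both depend on *prolonged*. The threshold of more than 4 days in 9.6 triggers evaluation, not a stop.
3. Sections 3.1 and 7.3 point to Section 7.6 as a source of further considerations on continuing or withdrawing treatment. Neither says that it overrides Table 3.

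Size, with the planned 8 patients treated: one patient handled differently changes a reported proportion by 1/8 = 0.125, that is 12.5 percentage points. In exposure, with a maximum of 5 cycles, a case (d) event in Cycle 1 leads to no further cycles under 7.6.1 and to as many as 5 - 1 = 4 under Table 3.

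**The case against.** The best reply is that a specific rule prevails over a general one. Table 3 is titled as a recommendation, and Section 5.4 leaves reduction or interruption to the investigator's evaluation. Section 7.6.1 names the toxicity and requires a permanent stop, and two sections direct readers to 7.6. A careful investigator would probably follow the specific text. That is a natural reading, and it makes it too strong to say that sites could not decide at all. But it is an inference. Sections 7.6.1 and 9.6 are themselves worded as what *should* be done, Section 9.1.3 cites 9.6 as the place where measures against anticipated toxicities are set out, and Table 3 gives special rows to other toxicities. A user of the table could reasonably conclude that neuropathy belongs in the generic rows.

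Two stronger readings are tempting, and the documents do not support them.

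- *All three passages contradict one another.* They do not: 7.6.1 and 9.6 fit together, and purely sensory Grade 2 neuropathy shows no clear conflict.
- *A patient who enters with Grade 2 motor neuropathy would be recorded as treatment-limited for a pre-existing condition.* Section 9.2.1 defines an adverse event in terms of new or exacerbated conditions, and Section 10.2.2 requires onset or worsening from baseline. The 9.6 weakness rule requires attribution to the drug, and the 7.6.1 list concerns toxicities that occur. Entry may also be narrower than it looks, since criterion 3 also covers clinically significant neurologic deficit and Inclusion 5 asks for recovery from short-term major toxicity. What remains is that the Grade 2 interruption sentence in 9.6 has no such qualifier, so how it applies to unchanged baseline neuropathy should be made clear.

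**Conclusion.** The contradiction is real and lies between Table 3 and the other two sections. It covers Grade 3 neuropathy that improves within 3 days (restart against permanent stop) and Grade 2 neuropathy with a motor component (half rate against interruption). In addition, *prolonged* is undefined wherever it decides a permanent stop. This should be corrected because the instructions bear directly on patient safety.

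The statistical size is one patient in 8, or 12.5 percentage points, on whichever of the interruption or discontinuation proportions is affected; it assumes 8 treated patients. A reader might infer that every neuropathy case moves the discontinuation rate by that amount. It does not: at Grade 1, at purely sensory Grade 2, and at Grade 2 that is neither prolonged nor accompanied by prolonged weakness, no passage discussed here requires a permanent stop. Nor can the chance that the conflict arises be calculated, because Section 9.6 describes neuropathy only as occasional and gives no rate by grade or type. The analyses are descriptive, so no test or error rate is affected.

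**What to change.** The sponsor's clinical experts should reconcile Section 5.4 (Table 3), Section 7.6.1 and Section 9.6 so that each grade and type of peripheral neuropathy, motor or sensory, has a single instruction. The protocol should then:

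- state which passage governs where the generic rows of Table 3 also apply;
- define *prolonged*;
- make clear how these passages apply to a patient who enters with the Grade 2 neuropathy that exclusion criterion 3 does not clearly bar.

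No clinical rule is proposed here, and the choice among the existing ones belongs to those experts. The cost is a wording amendment, handled under Section 14.2.1, with no new assessments and no change to the sample size.

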7.3. Treatment Period

Patients enrolled by the sponsor will be treated as described in Section 5.2.

Refer to Section 7.6 for additional considerations regarding treatment continuation and withdrawal.

Assessments before the start of dinutuximab beta infusion on Day 1 of each cycle:

- Oxygen-Saturation measurement
- Physical examination including vital signs, height, and weight
- Performance status
- 12-Lead ECG
- Chest X-ray
- Complete blood count including differential count*
- Biochemistry*

- Urinalysis*
- Pregnancy test in WOCBP
- Blood sampling for PK (30 minutes before infusion) in Cycle 1, 2, 3 and 4

*If clinical chemistry, hematology, coagulation and urinalysis at screening are not performed ≤ 7 days before study drug administration on Day 1 of Cycle 1, these tests should be repeated and reviewed before study drug administration. After Day 1 of Cycle 1, results are to be reviewed within 72 hours before study drug administration.

Assessments during dinutuximab beta infusions:

- Performance status (on each infusion day)
- Blood sampling for PK (infusion starting time ±1 hour on Day 3 and Day 8 in Cycle 1)
- The following assessments must be regularly repeated during dinutuximab beta infusions according to routine medical care procedures to ensure safe treatment of the patients:
 - Physical examination including vital signs
 - Complete blood count (including differential count) and biochemistry on Day 8
- Electrocardiography (ECHO) or multigated acquisition scan (MUGA) scan as clinically indicated

On Day 11 of each cycle, evaluations and blood sampling must be done just before the end of dinutuximab beta infusion, ie, within a couple of minutes before the end of infusion. Evaluations must include the following:

- Physical examination including vital signs
- Performance status
- 12-Lead ECG
- Complete blood count (including differential count) and biochemistry
- Blood sampling for PK (5 minutes before the end of infusion) in Cycle 1, 2, 3 and 4

Assessments after dinutuximab beta infusions:

- Complete blood count (including differential count) and biochemistry (Days 15, 22, and 29)
- Blood samples for PK (Day 15 and Day 22 [optional], and Day 29 in Cycle 1)

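### Protocol Section 9.6 and Table 3 give different instructions for a Grade 4 cytopenia found while the infusion is running

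*Protocol*

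**What the plan says.** Protocol Section 9.6, under hematologic toxicities, names these events as known effects of the antibody: "Occurrence of hematologic toxicities such as erythropenia, thrombocytopenia, or neutropenia has been reported with dinutuximab beta". It then says that Grade 4 events improving to Grade 2 or lower, or to "baseline values by start of next treatment course do not require dose modification".

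Protocol Section 5.4, Table 3, has a row for any adverse reaction of Grade 3 or higher. It begins "Interrupt infusion and administer supportive measures. Resume infusion at 50% rate", on condition that the reaction resolves or improves to Grade 1 or 2 within 3 days of onset. If half rate is tolerated for at least a day, a return to full rate may be considered. The row ends in two branches. At half rate, "If toxicity (≥ Grade 3) recurs at 50% dose reduction, treatment should be discontinued". After a recurrence at full rate, the infusion is stopped, the dose is halved if the toxicity improves within 3 days, and full dose is not tried again.

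The last row of Table 3 covers, among other things, "any other Grade 4 toxicity (which does not recover to Grade 1 or 2 or baseline within 5 weeks". There the infusion is discontinued and the sponsor is contacted about the next cycle.

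Protocol Section 7.3 schedules a count while the infusion is running: "Complete blood count (including differential count) and biochemistry on Day 8".

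**The concern.** An investigator who sees a drug-related Grade 4 cytopenia on Day 8 can find two answers in the protocol. Table 3 says to act now, and its row is not limited by organ system. Section 9.6 says no modification is needed, on a condition that only the following weeks can settle. Section 9.6 cannot be set aside as background, because Section 9.1.3 names it as the place where measures against anticipated toxicities are set out.

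Safety and tolerability form a primary objective. The outputs that depend on this decision are planned: interruption, delay and discontinuation because of adverse events (Protocol 10.2.1 and 10.2.2), dose reductions, interruptions and relative dose intensity (SAP 6.6.1), and adverse events leading to reduction, interruption or discontinuation (SAP 6.6.2). If sites resolve the conflict differently, these summaries partly reflect which passage each site followed.

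**Working it through.** The plan has no figure of its own to reproduce here. The check sets the passages side by side, with a little arithmetic for timing and scale.

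| | Section 9.6 | Table 3, any reaction ≥ Grade 3 | Table 3, last row |
|---|---|---|---|
| Grade | 4 only | 3 or higher | 4 |
| Scope | Hematologic | Any | Listed events and any other Grade 4 |
| Recovery target | Grade 2 or lower, or baseline | Resolved, or Grade 1 or 2 | Grade 1 or 2, or baseline |
| Recovery horizon | Start of next course | 3 days from onset | 5 weeks |
| Action | No modification if recovered | Interrupt; half rate if recovered; discontinue on recurrence at half rate | Discontinue if not recovered |

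**Overlap.** A Grade 4 cytopenia judged drug-related is both a hematologic toxicity under Section 9.6 and a reaction of Grade 3 or higher under Table 3. The first two columns both apply to it and prescribe different actions.

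**Does the last row settle it?** It concerns toxicity that does not recover. That is compatible with Section 9.6, which concerns toxicity that does. A recovering Grade 4 cytopenia is therefore left under the general row.

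**Timing.** Cycles last 35 days, so the next course starts nominally on Day 36. From Day 8 that is 36 − 8 = 28 days, or 25 to 31 days with the ±3-day Day 1 window of Section 8.6. The Section 9.6 condition cannot be known on Day 8. The general row asks for interruption at once and judges recovery at 3 days.

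**When it can arise.** Day 8 is the one count scheduled in mid-infusion. The Day 11 count is taken just before the infusion ends. On Days 15, 22 and 29 there is normally no infusion to interrupt.

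**Scale for one infusion.** The planned rate is 10 mg/m²/day for 10 days. At the start of Day 8, 7 × 10 = 70 mg/m² has been given and 100 − 70 = 30 mg/m² remains.
- *Ceiling:* if the infusion is interrupted then and not resumed, 30 mg/m² is lost. That is 30% of the cycle and 30 ÷ (5 × 100) = 6% of the five-cycle plan, which is the denominator for relative dose intensity in SAP 6.6.1.
- *Floor:* zero. Section 5.4 allows the infusion to be prolonged, or run at up to 3 mL/h against the usual 2 mL/h, so that the total dose is given. At half rate throughout, the remainder takes 30 ÷ 5 = 6 days in place of 3.

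**Scale for the counts.** With 8 treated patients, one patient is 1 ÷ 8 = 12.5 percentage points.

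**The case against.** The best reply is that the passages can be read together. Section 9.6 ties its condition to the start of the next course, so it may be a rule for that course, while Table 3 governs the infusion in progress. On that reading the unknown outcome on Day 8 is no difficulty, because laboratory results are reviewed before each cycle's dosing. The 5-week row supports it: five weeks is one cycle, and the recovery target nearly matches. Alternatively, Section 9.6 is a specific rule that overrides a general default. Table 3 already has specific rows that depart from the general one, such as hypersensitivity, where the infusion resumes at the original rate.

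Both readings are possible, but neither is stated, and they lead to opposite actions on Day 8. The exception reading also has an odd result. Section 9.6 names only Grade 4, so a Grade 3 cytopenia would trigger interruption while a recovering Grade 4 cytopenia would not.

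Several limits on the concern do stand. Table 3 is titled as a recommendation, and the lead-in to Section 5.4 is permissive and rests on the investigator's evaluation. The analyses are descriptive. The 12.5 points would apply to any ambiguity touching one patient; they do not measure this one in particular.

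Stronger conclusions are tempting, but the documents do not support them:
- *That Section 9.6 also conflicts with Table 3 for Grade 3 cytopenia.* It says nothing about Grade 3.
- *That Table 3 means half rate for the rest of the infusion, or discontinuation on any recurrence.* It allows a return to full rate, and discontinues only on recurrence at half rate.
- *That Cmax or AUC will be distorted.* No effect has been calculated. The end-of-infusion sample follows the actual end of infusion, and SAP 6.7 uses actual dose and draw times.
- *That the situation is bound to occur.* Section 1.2.3 lists cytopenias among commonly reported events, without their grades.

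**Conclusion.** The conflict is real but narrow. For a drug-related Grade 4 cytopenia present during an infusion, chiefly on the Day 8 count, Section 9.6 and the general row of Table 3 give different instructions, and nothing in the protocol says which prevails. Each patient handled differently moves an interruption, reduction or discontinuation rate by 12.5 points, assuming 8 treated patients. The dose at issue in that infusion lies between 0 and 30 mg/m², assuming full rate without interruption up to the start of Day 8. Where it falls depends on whether the infusion is resumed and made up, so no loss of total dose and no PK effect is established. How many patients would be affected cannot be estimated from the documents. It should be corrected, because the outputs concerned bear on a primary objective and the correction is simple.

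**What to change.** Reconcile Table 3, including its 5-week Grade 4 row, with Section 9.6:

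1. State in Table 3 whether hematologic toxicities fall under the row for any reaction of Grade 3 or higher.
2. State whether the Section 9.6 sentence governs the infusion in progress, the next course, or both.
3. Cross-reference the two passages.
4. Word the rule so that it rests on information available when the decision is made.

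Which clinical rule applies is for the sponsor to decide. The cost is a change of protocol wording, with no new assessments, no change in sample size and no change to the SAP's methods.
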